### 2.4. Secondary Endpoint(s)

#### Efficacy:

Subjects were to be randomized 3:3:1 to one of three treatment arms:

1. OE 10 mg amlodipine besylate tablet + OE 200 mg celecoxib capsule;
2. OE 10 mg amlodipine besylate tablet + matched placebo for OE celecoxib capsule;
3. Matched placebo for OE amlodipine tablet + matched placebo for OE celecoxib capsule.

A serial gatekeeping strategy was to be used to evaluate the effect of amlodipine tablets (10 mg) and celecoxib capsules (200 mg) given together on secondary efficacy endpoints. If and only if the

statistical significance was achieved for the primary efficacy endpoint, a secondary hierarchical analysis was to be used to evaluate the endpoints listed below, and was only to proceed to the next endpoint in the list if the alpha is met for the prior analyses.

1. Difference in mean change in body weight from baseline (Day 0) to Day 14 measurement (or if a LOCF is required, the Day 7 measurement) between treatment arms [amlodipine tablets (10 mg) and celecoxib capsules (200 mg) given together (arm 1), amlodipine tablets (10 mg) given alone (with matched celecoxib placebo) (arm 2), and placebo (arm 3)];
2. Difference in the mean reduction in SBP24h from the baseline (Day -1 to Day 0) ABPM measurement to the Day 13 to Day 14 ABPM measurement (or if a LOCF is required, the Day 6 to Day 7 ABPM measurement) between subjects treated with amlodipine tablets (10 mg) and celecoxib capsules (200 mg) given together (arm 1) and amlodipine tablets (10 mg) given alone (with matched celecoxib placebo) (arm 2);
3. Difference in the mean reductions in DBP24h from the baseline (Day -1 to Day 0) ABPM measurement to the Day 13 to Day 14 ABPM measurement (or if a LOCF is required, the Day 6 to Day 7 ABPM measurement) between subjects treated with amlodipine tablets (10 mg) and celecoxib capsules (200 mg) given together (arm 1) and amlodipine tablets (10 mg) given alone (with matched celecoxib placebo) (arm 2);
4. Difference in the mean change in creatinine clearance from baseline (Day 0) to the Day 14 measurement (or if a LOCF is required, the Day 7 measurement) between subjects treated with amlodipine tablets (10 mg) and celecoxib capsules (200 mg) given together (arm 1) and amlodipine tablets (10 mg) given alone (with matched celecoxib placebo) (arm 2).

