
Statistical Methods for Secondary Efficacy Analysis:
	
A serial gatekeeping strategy will be used to evaluate the effect of amlodipine tablets (10 mg) and celecoxib capsules (200 mg) given together on secondary efficacy endpoints. If and only if the primary blood pressure efficacy endpoint is statistically achieved, a secondary hierarchical analysis will be used to evaluate the endpoints listed below, and will only proceed to the next endpoint in the list if the alpha is met for the prior analyses.
 
 1. Difference in mean change in body weight from baseline (Day 0) to Day 14 (or Day 7 for subjects withdrawn from treatment at Day 7) between treatment arms [amlodipine tablets (10 mg) and celecoxib capsules (200 mg) given together (arm 1), amlodipine tablets (10 mg) given alone (with matched celecoxib placebo) (arm 2), and placebo (arm 3)]; 2. Difference in the mean reduction in SBP_{24h} from the baseline (Day -1 to Day 0) ABPM measurement to the Day 13 to Day 14 ABPM measurement (or to the Day 6 to Day 7 ABPM measurement for subjects withdrawn from treatment at Day 7) between subjects treated with amlodipine tablets (10 mg) and celecoxib capsules (200 mg) given together (arm 1) and amlodipine tablets (10 mg) given alone (with matched celecoxib placebo) (arm 2); 3. Difference in the mean reduction in DBP_{24h} from the baseline (Day -1 to Day 0) ABPM measurement to the Day 13 to Day 14 ABPM measurement (or to the Day 6 to Day 7 ABPM measurement for subjects withdrawn from treatment at Day 7) between subjects treated with amlodipine tablets (10 mg) and celecoxib capsules (200 mg) given together (arm 1) and amlodipine tablets (10 mg) given alone (with matched celecoxib placebo) (arm 2); 4. Difference in the mean change in creatinine clearance from baseline (Day 0) to Day 14 (or Day 7 for subjects withdrawn from treatment at Day 7) between subjects treated with amlodipine tablets (10 mg) and celecoxib capsules (200 mg) given together (arm 1) and amlodipine tablets (10 mg) given alone (with matched celecoxib placebo) (arm 2). 
Analysis of variance (ANOVA) will be utilized to compare body weight changes among the three treatment arms. Change in body weight will be the response with treatment arm

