4.3 Withdrawal of Subjects

A subject may choose to withdraw from this study at any time for any reason without penalty of jeopardizing their health care or loss of benefits to which the subject is otherwise entitled.

Subjects will be withdrawn from this study if one or more of the following events occur:

1. Subject requests to be withdrawn from study;
2. Allergic reaction or hypersensitivity reaction to the study drugs;
3. The subject's BP is too elevated for them to continue safely in the study (i.e., SBP_{24h} > 169 mmHg or DBP_{24h} > 110 mmHg);
4. AE (PTAE or TEAE) that in the judgment of the Investigator poses unacceptable risk to the subject;
5. Intercurrent illness that requires treatment that is not consistent with the protocol requirements, or intercurrent illness or the associated treatment that in the judgment of

the Investigator poses a significant risk to the subject for continued participation in the study;

6. Pregnant or suspected of being pregnant;
7. Use of prohibited medication (listed in Section 5.6) that in the judgment of the Investigator and Sponsor's Medical Monitor poses a significant risk to the subject for continued participation in the study or that will interfere with the interpretation of the results of this study;
8. Significant protocol violation or noncompliance on the part of the subject or the Investigator including inability to correctly use the ABPM;
9. Sponsor terminates the study or the Investigational Site terminates the study at their site;
10. Any other reason that in the judgment of Investigator poses unacceptable risk to the subject.

If a subject is withdrawn from the study, the date and reason will be recorded in the source documents and the case report form (CRF), and the Day 14 and Day 28 study evaluations will be performed if feasible. Any subject withdrawn due to a study drug-related TEAE (adverse reaction or suspected adverse reaction per the definitions in Section 8.1.3) will be followed until resolution or stabilization of the event.

If subject becomes pregnant or is suspected of being pregnant, study drugs will be discontinued immediately, and the subject will be referred to an obstetrician/gynecologist experienced in reproductive toxicity for further evaluation and counseling. The subject will be followed until delivery or other termination of pregnancy for outcome.

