5. Subjects will be provided back their diary and instructed to record any concomitant medications taken and details of study drug administration;
6. Instruct subjects to return to the clinic in 6 days (on the morning of Day 13), and to bring the completed diary and study drug containers with any unused study drug.

If during the Day 7 visit, the subject's BP is too elevated for them to continue safely in the study (i.e., SBP_{24h} > 169 mmHg and/or DBP_{24h} > 110 mmHg), blood will be drawn for renal profile testing (see Section 8.5). The subject will be instructed to cease taking study drugs, instructed to resume taking their prescribed BP medication as directed by the study doctor or general practitioner, given back their diary and instructed to record any concomitant medications taken between visits, and instructed to return to the clinic in 7 days (Day 14).

6.5 Study Day 13

Subjects will return to clinic on the morning of Day 13 (except for those discontinued from study drug due to excessive hypertension or other safety reasons at Day 7) and will undergo the following procedures:

1. Solicit history of TEAEs since the previous visit;
2. Review diary for details of study drug administration and concomitant medications since the previous visit;
3. Collect study drug containers and count and record any unused study drug;
4. Provide subjects with an ABPM, instruct in its use, and check the positioning of the ABPM.

Following the placement of the ABPM, the subjects will be administered their Day 13 dose of study drugs (final dose) in the clinic. Prior to leaving the clinic, the following procedures will be performed:

1. Instruct subjects to wear the APBM at all times for the next 25 hours;
2. Subjects will be given back their diary and instructed to record any concomitant medications taken between visits;
3. Instruct subjects to return to clinic the following day (on the morning of Day 14), and to bring the completed diary to the clinic.

6.6 Study Day 14

Subjects will return to clinic on the morning of Day 14. The following evaluations will be performed:

1. Solicit history of TEAEs since the previous visit;
2. Review diary for details of concomitant medications since the previous visit;
3. Comprehensive physical examination (see Section 8.2);
4. Body weight while only wearing underwear and a light gown;
5. Vital signs (BP, pulse rate, respiration rate, and oral body temperature);

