## 7. Statistical Methodology

### 7.1. Handling of Missing Data

For ITT and mITT population, if at the time of the Day 7 clinic visit subjects have a too elevated BP to be able to continue safely in the study (i.e., SBP24h > 169 mmHg or DBP24h > 110 mmHg), blood will be drawn for renal profile testing, the study drug will be discontinued and the subjects will be instructed to resume taking their prescribed BP medication as directed by the study doctor or general practitioner. In case of missing data, LOCF techniques will be used as follows:

1. ITT population: LOCF from baseline (Day 0)
2. mITT population: LOCF from Day 6

Using this method, the end of study measurement is either Baseline, Day 6 or Day 13.

No specific analysis for withdrawn patients will be presented.

The number of patients with missing data will be presented under the “Missing” category, if present. Missing values will be included in the denominator count when computing percentages.

When continuous data are being summarized, only the non-missing values will be evaluated for computing summary statistics.

Missing or incomplete data will be treated as described in sections 5, 6.4, 6.5, 7.1, 7.9, 7.10. Other critical missing data will be discussed prior to treatment unblinding, if any. Decisions will be taken during the data review and will be fully documented in the Data Review Report.

The LOCF method of imputation will be applied for missing values in all ANCOVA models. This method will not be applied to the descriptive statistics.

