## 7.8. Secondary Efficacy Analysis

Per the protocol, a serial gatekeeping strategy was to be used to evaluate the effect of amlodipine tablets (10 mg) and celecoxib capsules (200 mg) given together on the secondary efficacy endpoints. If and only if the statistical significance was achieved for the primary efficacy endpoint, the secondary hierarchical analysis was to be used to evaluate the secondary endpoints (i.e., body weight,  $SBP_{24h}$ ,  $DBP_{24h}$ , and creatine clearance) and was only to proceed to the next endpoint in the list if the alpha is met for the prior analyses. While defining success at the secondary efficacy level will remain based on the hierarchical approach, regardless of the outcome, all four secondary efficacy endpoints (body weight,  $SBP_{24h}$ ,  $DBP_{24h}$ , and creatine clearance) will be analyzed for informational purposes and to allow comparisons to the trends and statistically significant differences observed in the prior trial (KIT-302-03-01).

For all secondary efficacy endpoints, the mean change has been computed considering the difference between the value at endpoint (Day 13 to Day 14 for ABPM endpoints and Day 14 for body weight and creatinine clearance) and the value at baseline (Day -1 to Day 0 for ABPM endpoints and Day 0 pre-dose for body weight and creatinine clearance) [Endpoint – Baseline].

1. Analysis of Variance (ANOVA) will be used to compare the changes in body weight among the three treatment arms. The omni-bus test will conclude if any differences exist with post-hoc comparisons identifying specific differences between treatment arms. Any statistically significant differences will be sufficient to pass this gate in the study-wide gate keeping strategy.

$$H_0: \Delta BW_1 = \Delta BW_2 = \Delta BW_3$$

$$H_1: \text{At least one difference, } \Delta BW_i - \Delta BW_j \neq 0$$

Where  $\Delta BW_1$  is the change, for subjects in arm 1, in body weight from the baseline measurement to the post-treatment measurement.  
 $\Delta BW_2$  is the change, for subjects in arm 2, in body weight from the baseline measurement to the post-treatment measurement.  
 $\Delta BW_3$  is the change, for subjects in arm 3, in body weight from the baseline measurement to the post-treatment measurement.

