### **Vital signs - BP**

Clinic visit average resting SBP and DBP (mmHg) will be summarized for the Safety population by treatment group at each applicable visit (Initial Screening Visit, Day 0, Day 7, Day 14, and Day 28) by descriptive statistics (n, mean, SD, median, and range). In addition, at each visit after baseline, change from baseline will be calculated and summarized by descriptive statistics (n, mean, SD, median, and range). Baseline will be Day 0 if available, otherwise, the Initial Screening Visit assessment will be used.

For each variable (average resting SBP and DBP) a comparison between treatment groups will be performed with an ANCOVA model with change from baseline to Day 14 as dependent variable, treatment as fixed effect and baseline as covariate. A LOCF method of imputation will be applied for missing values. In the event there is no Day 14 measurement, the Day 7 measurement will be carried forward. Baseline measurement is Day 0 (prior to study drug administration); however, in the event the Day 0 measurement is missing, the Initial Screening Visit measurement will be carried forward. The number of patients and the number of patients considered in the model will be provided by treatment. The adjusted means for treatments and the relative 95% CIs and p values will be presented. The difference between the adjusted means of the three treatment groups will be calculated with the relative 95% CI and p-value.

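### For subjects withdrawn at Day 7 for elevated BP, the SAP as worded admits an off-drug Day 14 value for body weight and creatinine clearance, where the protocol synopsis uses Day 7

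*SAP*

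**What the plan says.** **Protocol synopsis, secondary efficacy analysis.** Body weight is analysed from baseline "to Day 14 (or Day 7 for subjects withdrawn from treatment at Day 7) between treatment arms". The creatinine clearance item carries the same Day 7 rule.

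**Protocol 10.1.1.** LOCF and MMRM are introduced for one situation: study drug stopped at the Day 7 visit because BP is too high.

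**Protocol 6.4.** Such a subject stops study drug, is "instructed to resume taking their prescribed BP medication as directed by the study doctor or general practitioner, given back their diary", and returns on Day 14. Protocol 4.3 adds, for any withdrawn subject, that "the Day 14 and Day 28 study evaluations will be performed if feasible".

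**SAP 2.4.** Weight is taken at the "Day 14 measurement (or if a LOCF is required, the Day 7 measurement) between treatment arms", and creatinine clearance is worded the same way. SAP 7.8 gives the endpoint as "Day 14 for body weight and creatinine clearance", with no exception for subjects off drug.

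**SAP 7.1.** The section opens with the Day 7 high-BP withdrawal but then sets a different trigger: "In case of missing data, LOCF techniques will be used as follows". It adds: "The LOCF method of imputation will be applied for missing values in all ANCOVA models".

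**SAP 7.9, clinic BP.** "In the event there is no Day 14 measurement, the Day 7 measurement will be carried forward".

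**The concern.** The stated objective in both documents is change from baseline to end of treatment. A subject withdrawn at Day 7 for elevated BP ends treatment on Day 7. If a recorded Day 14 value switches LOCF off, the number analysed reflects a week without study drug and a week on whichever single agent the subject used before.

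Weight is the first test in the secondary hierarchy and creatinine clearance the fourth, so a misdefined value touches both ends of the chain. These withdrawals are triggered by the subject's BP on treatment, so their frequency can differ by arm and the resulting error need not cancel between arms.

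The same subject would also be scored at two different times: Day 6 to Day 7 for ambulatory BP, and Day 14 for weight and renal function.

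**Working it through.** The plan has no figure of its own to reproduce here. The check traces the rules, followed by an illustration of scale.

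**1. Is a Day 14 value available?** Yes, as a rule. The Day 7 high-BP withdrawal is called back on Day 14 (Protocol 6.4). The Day 14 visit includes weight, vital signs and serum chemistry (Protocol 6.6).

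**2. Is it off drug?** The Day 7 dose is taken at home before the visit, so time off drug at Day 14 is 14 − 7 = 7 days. A completer, whose last dose is on Day 13, is 14 − 13 = 1 day from the last dose.

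**3. Is there an on-drug alternative?** Yes. Weight and creatinine are both measured at Day 7 (Protocol 7.2 and 7.3).

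**4. Which value does each text select?**

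| Text | What brings in Day 7 | Value for a Day 7 high-BP withdrawal |
|---|---|---|
| Protocol synopsis | withdrawal at Day 7 | Day 7 |
| Protocol 10.2.4, read with 10.1.1 | LOCF, tied to that withdrawal | Day 7 |
| SAP 2.4 and 7.8, read with 7.1 | LOCF, tied to missing data | Day 14, read literally |
| SAP 7.9, clinic BP | no Day 14 measurement | Day 14, explicitly |
| SAP 2.3, primary endpoint | withdrawal at Day 7 | Day 6 to Day 7 recording |

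SAP 7.1 names Baseline, Day 6 and Day 13 as the possible end-of-study points. Those are ambulatory monitoring days, so the section gives no separate rule for weight or creatinine clearance.

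**5. Is the change declared?** SAP 1.3.9(h) mentions LOCF for missing vital signs. Nothing in SAP 1.3 covers the altered trigger for weight or creatinine clearance.

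**6. Scale (illustrative; the number of such withdrawals is not given).** With k affected subjects among n, and Day 14 values retaining a share r of the drug effect, the arm's mean change shrinks by (k/n)(1 − r). Take n = 45 (Protocol Appendix H; also 105 × 3/7):

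- r = 0: k = 1, 2, 5 gives 2.2%, 4.4%, 11.1%.
- r = 0.5: k = 1, 2, 5 gives 1.1%, 2.2%, 5.6%.

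The placebo arm enters the three-arm weight ANOVA. At the planned 3:3:1 it has 105/7 = 15 subjects, so one subject carries 1/15 = 6.7% of its mean. At the 6:6:1 reported in SAP 3.2, and taking 105 in total, it has 105/13 ≈ 8, so one subject carries 1/8 = 12.5%.

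For clinic SBP, assume that resumed medication lowers one such subject by 20 mmHg (range 10 to 30). The placebo mean then moves by 20/8 = 2.5 mmHg (10/8 = 1.3 to 30/8 = 3.8). In an active arm of 105 × 6/13 ≈ 48 it moves by 20/48 = 0.4 mmHg.

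**The case against.** The strongest reply is that SAP 2.4 never defines when LOCF is required. The exploratory analyses in SAP 1.3.4 and 7.10 apply LOCF to subjects withdrawn early, and SAP 7.1 opens with the Day 7 withdrawal. Items 2 and 3 of SAP 2.4 use the same parenthesis for 24-hour BP, where it does cover these subjects. Items 1 and 4 read the same way would give Day 7. SAP 2.4 also repeats Protocol 10.2.4 almost unchanged, so part of the mismatch lies within the protocol. This stands: for weight and creatinine clearance the fault is an unresolved ambiguity, not a certain error. It does not help clinic BP, where SAP 7.9 leaves no other reading.

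A second reply is that analysing the observed Day 14 value regardless of discontinuation is a legitimate treatment-policy choice. It is, but neither document states it for these endpoints, and it conflicts with the synopsis. The ITT argument in SAP 1.3.2 concerns who is analysed, not which measurement is used. For the safety ANCOVAs, which are specified as change to Day 14, the reply has more force.

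Stronger readings are tempting but not supported:

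- A reader might infer that every early stop is analysed a week or more off drug on resumed antihypertensives. Stops on Days 8 to 12 are 6 to 2 days off drug at Day 14. Resumption before Day 14 is stated only for high-BP withdrawals; otherwise Protocol 5.6 bars prior BP medication until then.
- A reader might infer that the ambulatory endpoints escape only by accident. SAP 2.3 expressly assigns the Day 6 to Day 7 recording for the primary endpoint.
- A reader might set the 2.5 mmHg placebo shift against the 2.1 mmHg placebo fall in the earlier trial. That fall is daytime ambulatory SBP; clinic BP here is a safety variable.

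**Conclusion.** The concern holds for subjects withdrawn at Day 7 for elevated BP. The protocol scores their weight and creatinine clearance at Day 7. The SAP's literal wording scores them at Day 14, off drug and on resumed medication, without declaring the change. For clinic BP the SAP says so outright. The primary endpoint is not affected.

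The size is unknown. On the illustration above, one or two such subjects in an arm of 45 shrink that arm's mean change by about 1% to 4%. A single subject weighs more in the placebo arm, which matters for the weight ANOVA but not for creatinine clearance, where only arms 1 and 2 are compared. No figure in the documents allows the shift in weight or creatinine clearance to be computed in their own units, and the number of such subjects may be zero. The case for acting rests on the undeclared conflict and on the outcome-dependent nature of these withdrawals, not on a demonstrated large bias. SAP version 4.0 is also dated after unblinding (SAP 1.5), so the choice should not be left to whoever programs the derivation.

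**What to change.** - **Weight and creatinine clearance (SAP 2.4, 7.1, 7.8).** Replace the LOCF condition with the synopsis rule: the Day 7 value for subjects withdrawn from treatment at Day 7. List their off-drug Day 14 values separately. Note in SAP 1.3 that this restores the synopsis rule and does not depend on results.
- **Clinic BP (SAP 7.9).** Apply the same Day 7 rule to Day 7 withdrawals, or report the Day 14 ANCOVA with and without their off-drug values.
- **Other safety ANCOVAs (weight, orthostatic BP, creatinine, BUN).** Keep Day 14, flag the off-drug values and show the result without them. A blanket rule of last value on drug would not work. BUN is not in the routine Day 7 panel and is drawn then only in the renal profile for high-BP withdrawals (Protocol 8.6). Subjects who stop before Day 7 have no scheduled on-drug value at all.

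If a treatment-policy analysis is preferred instead, state it and list it as a change from protocol.

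The cost is a few lines of SAP text and one derivation flag from the last-dose date already on the CRF (SAP section 5). The downside is that a few observed Day 14 values are listed rather than used in the main test.

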### 3. Study Design

This is a multi-center, randomized, double blind, placebo controlled trial to evaluate the effect of celecoxib on the efficacy, safety, and pharmacokinetics of amlodipine in subjects with existing hypertension requiring antihypertensive therapy.

Approximately 105 adult subjects who required and were currently using pharmacological therapy with a single agent that was not a calcium channel blocker to control their hypertension were to be randomized 3:3:1 to one of three treatment arms:

1. OE 10 mg amlodipine besylate tablet + OE 200 mg celecoxib capsule;
2. OE 10 mg amlodipine besylate tablet + matched placebo for OE celecoxib capsule;
3. Matched placebo for OE amlodipine tablet + matched placebo for OE celecoxib capsule.

All drugs were to be administered orally qd for 14 days (Days 0-13) for a total of 14 doses. With the exception of Day 0, when study drug intake was to be after determination of eligibility (and at least 25 hours after the Day -1 ABPM is initiated), Days 6 and 13, when study drug intake was to be at the time of fitting the ABPM (following fitting) and Day 7, when study drug intake was to be 24 h ± 1 h after the Day 6 dose, the subjects were to be instructed to take the study drugs between 07:00 and 10:00, and preferably at approximately the same time each day.

**Initial Screening Visit (Day -14 to -10):** Each subject was to be provided with oral and written information (ICF) describing the study and have any questions answered. Subjects that consented in writing to participate in the study were to undergo eligibility assessments, including complete medical history, comprehensive physical examination, height, body weight in underwear and light gown, BMI,

vital signs (BP, pulse rate, respiration rate, and oral body temperature), 12-lead ECG, hematology, serum chemistry, urinalysis, serum pregnancy test for women of childbearing potential (WCBP), urine drug screen, and record medications taken within 30 days prior to initial screening visit.

Subjects who met eligibility criteria based on the above initial screening visit procedures were to be instructed to cease taking their current BP medication. Monitoring for PTAEs was to begin upon completion of the initial screening visit procedures and continue through the 9 to 13 days of washout, the final screening visit on Day -1, and the baseline procedures on Day 0 (i.e., prior to the administration of the first dose of study drugs). Any untoward medical occurrence that initiated or worsened after completion of the initial screening visit procedures and before administration of the first dose of study drugs was to be recorded as a PTAE. Subjects were to be instructed to return to the clinic in 9 to 13 days.

**Final Screening Visit (Day -1)** Subjects were to return to the clinic after 9 to 13 days of washout for their final screening visit (Day -1). They were to undergo the following procedures: solicit for history of PTAEs since the previous visit and record medications taken since prior visit. Those who continued to meet eligibility criteria were to be given an ABPM, instructed in its use, and have the positioning of their ABPM checked. They were to be instructed to wear it at all times for the next 25 hours and to return to the clinic the following day.

**Study Day 0:** When the subjects returned to clinic the following day, the ABPM was to be collected and the data contained therein downloaded and analysed. If subjects were found to be hypertensive, based upon their ABPM measurement, they were to undergo additional baseline procedures as described below. If the subject's BP was too elevated for them to continue safely in the study (i.e.,  $SBP_{24h} > 169$  mmHg or  $DBP_{24h} > 110$  mmHg), the subject was not to be enrolled and they were to be instructed to resume taking their prescribed BP medication as directed by the study doctor or general practitioner. If the subject was found to be normotensive ( $SBP_{day} \leq 135$  mmHg), the subject was not to be enrolled. The subject's primary care doctor was to be informed that he/she had been found not to be hypertensive. No subject was to be randomized until these baseline ABPM data were reviewed and it was documented that the subject met entry BP criteria.

Subjects who met the BP criteria ( $SBP_{day} > 135$  and  $\leq 169$  mmHg and  $DBP_{day} \leq 110$  mmHg) following completion of the 10 to 14 day washout period were to undergo the following additional baseline procedures: solicit for history of PTAEs since the previous visit, targeted physical examination, body weight in underwear and light gown, vital signs, orthostatic hypotension evaluation, serum chemistry, and record medications taken since last visit. Subjects that continued to meet all eligibility requirements were to be enrolled in the study and randomized 3:3:1 to one of three treatment arms. The subjects were then to be administered their first dose of study drugs in the clinic.

Monitoring for TEAEs was to begin immediately following administration of the first dose of study drugs and was to continue throughout the study. Any untoward medical occurrence that initiated or worsened after the first dose of study drugs and within 14 days of the last dose of study drugs was to be recorded as a TEAE. Subjects were to remain in the clinic under observation for one hour following their first dose and were to be solicited for TEAE history prior to leaving the clinic. Subjects were to be provided with sufficient study drugs for the remainder of the 2-week treatment period, and instructed to take the study drugs qd in the morning. Subjects were to be provided with a diary and instructed to record any concomitant medications taken and details of study drug administration. Subjects were to be instructed to return to clinic the morning of Day 6.

**Study Day 6:** Subjects were to return to clinic on the morning of Day 6 and were to be solicited for history of TEAEs since the previous visit. The study drug containers were to be collected and unused

study drug counted and recorded. The diary was to be reviewed for details of study drug administration and any concomitant medications taken since the previous visit. Subjects were to be given an ABPM, instructed in its use, and have the positioning of their ABPM checked. The subjects were then to be administered their Day 6 dose of study drugs, and instructed to wear the ABPM at all times for the next 25 hours. Subjects were to be given back their remaining study drug supply and diary, instructed to record any concomitant medications taken and details of study drug administration, and to return to clinic the following day.

**Study Day 7:** The Day 7 study drugs were to be self-administered at home within 24 hours  $\pm$  1 hour from the Day 6 dose. Subjects were to return to clinic on the morning of Day 7 (after the home administration of study drugs). The diary was to be reviewed for any concomitant medications taken and for details of study drug administration since the previous visit. The study drug containers were to be collected and unused study drug counted and recorded. Subjects were to be solicited for history of TEAEs since the previous visit. A targeted physical examination was to be performed and body weight in underwear and light gown and vital signs were to be measured. An orthostatic hypotension test was to be performed. Subjects were to have BP as measured by the ABPM recorded and the ABPM collected. Subjects were to have blood collected for measurement of creatinine (and calculation of creatinine clearance) and electrolytes.

If the Investigator determined that it was safe for the subject to continue in the study, the subject was to have their remaining study drug supply returned to them, and instructed to take the study drugs at home on Days 8-12, between 0700 and 1000 hours, and preferably at approximately the same time each day. Subjects were to be given back their diary and instructed to record any concomitant medications taken and details of study drug administration, and instructed to return to the clinic in 6 days (on the morning of Day 13).

If the subject's BP was too elevated for them to continue safely in the study (i.e.,  $SBP_{24h} > 169$  mmHg or  $DBP_{24h} > 110$  mmHg), blood was to be drawn for renal profile testing. The subject was to be instructed to cease taking study drugs, instructed to resume taking their prescribed BP medication as directed by the study doctor or general practitioner, given back their diary and instructed to record any concomitant medications taken between visits, and instructed to return to the clinic in 7 days (Day 14).

**Study Day 13:** Subjects were to return to clinic on the morning of Day 13 (except for those discontinued from study drug due to excessive hypertension or other safety reasons) and were to be solicited for history of TEAEs since the previous visit. The diary was to be reviewed for details of study drug administration and any concomitant medications taken since the previous visit. The study drug containers were to be collected and any unused study drug counted and recorded. Subjects were to be given an ABPM, instructed in its use, and have the positioning of their ABPM checked. The subjects were then to be administered their Day 13 dose of study drugs (final dose), and instructed to wear the ABPM at all times for the next 25 hours. Subjects were to be given back their diary and instructed to record any concomitant medications taken between visits, and instructed to return to clinic the following day.

**Study Day 14:** Subjects were to return to clinic on the morning of Day 14. The diary was to be reviewed for any concomitant medications taken since the previous visit. Subjects were to be solicited for history of TEAEs since the previous visit. A comprehensive physical examination was to be performed and body weight in underwear and light gown and vital signs were to be measured. BP as measured by the ABPM was to be recorded and the ABPM collected. An orthostatic hypotension evaluation was to be performed. The following additional evaluations were to be performed: 12-lead ECG, hematology, serum chemistry, urinalysis, and urine pregnancy test for WCBP.

In addition, subjects were to have a blood sample collected 24 hours  $\pm$  1 hour post-dose for measurement of amlodipine concentrations. Only subjects enrolled at Investigational Sites that had UV-shielded lights were to participate in the PK blood collections. Due to the design of the trial (randomized, double-blind, placebo-controlled), this blood sample was to be collected and analyzed for all participating subjects, regardless of whether they were in a treatment arm that received amlodipine.

Following the Day 14 evaluations, the subjects were to be instructed to resume taking their prescribed BP medication as directed by the study doctor or general practitioner, given back their diary and instructed to record any concomitant medications taken between visits, and instructed to return to the clinic in 14 days (Day 28).

**Study Day 28:** Subjects were to return to clinic on Day 28 for their final study visit (follow-up visit). The diary was to be reviewed for any concomitant medications taken since the prior visit. Subjects were to be solicited for history of TEAEs since the previous visit. A targeted physical examination was to be performed and vital signs were to be measured. For subjects whose study drugs were discontinued at Day 7, this follow-up visit was still occur on Day 28 (i.e., these subjects were to return to the clinic for both the Day 14 and Day 28 visits).

The schedule of events is provided in the table below.

Event	Screening		Baseline/ 1 st Dose	Remainder of Treatment Period			Follow-up	
	Initial Screening Visit	Final Screening Visit		Day 6	Day 7	Day 13	Day 14 (a)	Day 28 (a)
	Day -14 to -10	Day -1						
Informed consent (b)	X							
Record demographic data	X							
Complete medical history	X							
Monitor for pretreatment adverse events (PTAEs) (k)	X	X	X					
Record prior medications	X	X	X					
Record concomitant medications (CM)			X	X	X	X	X	X
Height and BMI	X							
Body weight while only wearing underwear and a light gown	X		X		X		X	
Comprehensive physical examination (c)	X						X	
Targeted physical examination (d)			X		X			X
Vital Signs (e)	X (e)		X		X		X	X
Provide ABPM and instruct on use		X		X		X		
25-hour monitoring of BP via ABPM (f)		X		X		X		
Orthostatic hypotension evaluation			X		X		X	
12-lead ECG	X						X	
Hematology (g)	X						X	
Serum chemistry (g)	X		X		X (g)		X	
Serum pregnancy test (h)	X							
Urine pregnancy test (h)							X	

Event	Screening		Baseline/ 1 st Dose	Remainder of Treatment Period			Follow-up	
	Initial Screening Visit	Final Screening Visit		Day 6	Day 7	Day 13	Day 14 (a)	Day 28 (a)
	Day -14 to -10	Day -1						
Urinalysis (g)	X						X	
Urine drug screen (g)	X							
Review inclusion/exclusion criteria	X	X	X					
Randomization (i)			X					
Administer study drug in clinic (j)			X	X		X		
Provide diary to record CMs and study drug details			X					
Review diary				X	X	X	X	X
Collect study drug containers/capsule count				X	X	X		
Monitor for treatment emergent adverse events (TEAEs) (k)			X	X	X	X	X	X
Blood collection for PK (l)							X	

- a. If a subject was discontinued from study drug early, all study evaluations described for Day 14 and Day 28 were to be performed if feasible. Study drug-related AEs (adverse reaction or suspected adverse reaction per the definitions in Section 8.1.3 of the protocol) were to be followed until resolution or stabilization.
- b. ICF must have been signed prior to performing any other screening evaluations
- c. Comprehensive physical examination was to include the following organ or body system assessments: skin; head, eyes, ears, nose, and throat; thyroid; lungs; cardiovascular; abdomen (liver, spleen); lymph nodes; and extremities, as well as an abbreviated neurological exam
- d. Targeted physical examination were to specifically target the cardiovascular system and were to include vital signs, plus an examination of the extremities to check for the presence of edema, as well as an examination to document any other evidence of a cardiovascular problem. Any areas of concern from the medical history or noted on the prior physical examination or indicated by subject symptoms or other findings as determined by the Investigator or designee may also have been examined.
- e. BP, pulse rate, respiration rate, and oral body temperature. At the Initial Screening Visit, the arm with the higher average clinical visit systolic BP was to be determined and used for all further BP measurements including ABPM measurements (see Section 8.3 of the protocol).

- f. BP was to be continually recorded with an ABPM on one to three 25-hour periods during the trial: Day -1 to Day 0, Day 6 to Day 7, and Day 13 to Day 14 (see Section 7.1 of the protocol for further detail)
- g. See Appendix B of the protocol for a list of the specific hematology, serum chemistry, urinalysis, and drug tests. The serum chemistry tests at Day 7 was to be limited to creatinine (and calculation of creatinine clearance) and electrolytes (sodium, bicarbonate, calcium, chloride, phosphorous, and potassium), rather than the full panel listed in Appendix B.
- h. Only for WCBP
- i. Only after all other baseline procedures have been completed and the subject's eligibility was confirmed. Subjects were to be randomized 3:3:1 to one of three treatment arms (see Section 5.2 of the protocol)
